Cognitive tasks have been split between the two appointments to minimize cognitive fatigue.

Baseline and Post Visit 2 MRI Assessments: fMRI scanning sessions will occur at baseline and post-training assessment points on a General Electric MR 750 3-Tesla MRI scanner using multiband protocols established by the Human Connectome Project. Each session will consist of a three-plane scout scan (16s), field mapping, a standard anatomic al protocol for standardizing and localizing activation maps) using 3D MPRAGE (TR=2500ms; TE=2ms; TI=1s; flip angle=80; FOV=256x256; 208 sagittal slices; 1mm isotropic voxels [6 minutes 9 seconds]). Functional runs will use a series of BOLD scans collected with Gradient-echo echo planar imaging (EPI) T2* (TR=800ms; TE=30ms; flip angle=520; FOV=216x216mm; 60 axial slices; 2.4mm isotropic voxels). These parameters enable us to cover the entire brain. Functional tasks will include:

Reading Span. This task assesses cognitive control under conditions of high and low interference. In this task, participants try to memorize stimuli presented on the screen (e.g., letters, numbers) while simultaneously solving secondary puzzles (e.g., decide if this sentence makes sense or not). Behavioral outcomes from this task include overall task performance (% correctly recalled stimuli) and reaction times.

Emotional working memory task. In this task, participants view neutral and valenced words, followed by a delay that contains distractor word stimuli. Participants try to remember the words presented to them. Behavioral outcomes from this task include overall task performance (% correctly recalled stimuli) and reaction times.

Participants may also complete resting state (approximately 10 minutes) and additional structural scans (approximately 5 minutes) if time permits, which do not require participant responses. Participant scans will be booked in a one hour block. Participants will complete both scans if they have 15 minutes left following the tasks. They will complete only resting state if they have 10 minutes left following the tasks. They will complete only the structural scan if they have 5 minutes left following the tasks.

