Secondary outcome of cognitive training neural generalization effects: Images will be co-registered using AFNI's 3dvolreg program conducted with the EPI image that results in the smallest adjustment in motion parameters (x, y, z, roll, pitch, yaw). Data will be preprocessed for despiking, censoring outliers, and blurred with an applied Gaussian blur of 4.0mm and transformed into MNI coordinates. The time series of motion parameters will be used to obtain an average for these six motion parameters for each subject, and subjects will be excluded if the average in any one of these parameters exceeds 2 standard deviations from the mean of the distribution of these average motion parameters. A multivariate regressor approach detailed below will be used to relate changes in EPI intensity to differences in task characteristics. A 0-1 reference function will be convolved with a gamma-variate function to model a prototypical hemodynamic response (6-8 second delay) and to account for the temporal dynamics of the hemodynamic response (typically 12-16 seconds). The convolved time series will be normalized and used as a regressor of interest. A series of regressors of interest, polorts for detrending, and the motion regressors will be entered into the AFNI program 3dDeconvolve to determine the height of each regressor for each subject. Voxel-wise normalized relative signal change will be obtained by dividing the regressor coefficient by the sum of the zero-order regressor and the mean first-order regressor. AFNI 3dREML will be used to reduce the false positives induced by cross correlations of the time series.

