10. HUMAN SUBJECTS

The current study will recruit 95 individuals enrolled at UCSD with a diagnosis of mood, anxiety, or traumatic stress disorder from psychiatric and primary care clinics. The study will overrecruit with the goal of randomizing 75 individuals for a final evaluable sample of 65.

Inclusion criteria will include:

- 1) age 21-55
- 2) fluent in English (sufficient to understand and complete assessments in English)
- 3) diagnosis of mood, anxiety, or traumatic stress disorder
- 4) clinically elevated repetitive negative thinking

- 5) outpatient status
- 6) 6-week stability if taking SSRI medications

Exclusion criteria will include:

- 1) past year diagnosis of severe alcohol or moderate or greater substance use disorder
- 2) lifetime history of psychotic or bipolar I disorder
- 3) acute suicidality necessitating immediate clinical intervention
- 4) neurodegenerative or neurodevelopmental disorders
- 5) history of moderate or severe traumatic brain injury or other known neurological condition
- 6) sensory deficits that would preclude completing tasks
- 7) conditions unsafe for completing MRI scanning (e.g., metal in body)
- 8) currently receiving psychosocial treatment
- 9) currently receiving psychiatric pharmacotherapy, except SSRIs

There are no inclusion/exclusion criteria pertaining to gender, ethnic background, or health status aside from MRI safety requirements stated above.

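### The fMRI motion exclusion, read literally, scores average head position rather than amount of movement, so balanced movement can cancel and a single settle can score high.

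*Combined protocol and SAP*

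**What the plan says.** The rule is in section 9, in the paragraph on the secondary outcome of neural generalization. Registration uses 3dvolreg, "conducted with the EPI image that results in the smallest adjustment in motion parameters (x, y, z, roll, pitch, yaw"). For the summary score the plan says: "The time series of motion parameters will be used to obtain an average for these six motion parameters for each subject". The exclusion follows: "subjects will be excluded if the average in any one of these parameters exceeds 2 standard deviations from the mean of the distribution" of those averages. The six parameters are therefore averaged and tested one by one; they are not pooled.

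The same paragraph handles motion in two other ways. At volume level: "Data will be preprocessed for despiking, censoring outliers, and blurred with an applied Gaussian blur of 4.0mm". At model level: "A series of regressors of interest, polorts for detrending, and the motion regressors will be entered into the AFNI program 3dDeconvolve". It sets no limit on the share of censored volumes, so the 2 SD rule is the only participant-level motion exclusion. Section 10 recruits "with the goal of randomizing 75 individuals for a final evaluable sample of 65".

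The plan does not say whether signs are kept before averaging, gives no limit in millimetres or degrees, and states no expected number of exclusions.

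**The concern.** The six parameters are directional adjustments to a reference image. Averaged over time as written, they describe where the head sat, not how much it moved. Movement to either side of the reference cancels, and choosing the reference image that needs the least adjustment pulls a restless participant's average towards zero. A participant who shifts once and then lies still carries a lasting offset and can score as an outlier.

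The rule decides who enters the group-by-time fMRI model, and Aim 1 names fMRI as one of its two measures of executive functioning. A score that ranks participants wrongly can discard usable scans and keep contaminated ones.

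**Working it through.** The plan gives no figure to reproduce. All movement sizes below are assumptions.

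**1. Two constructed traces** (one axis, 750 volumes, which is 10 minutes at the stated "TR=800ms; TE=30ms"; the run length is assumed).

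- Oscillation of amplitude 2 mm with a 10-volume period, x(t) = 2 sin(2πt/10). The signed mean is 0.00 mm because each period sums to zero. The mean absolute displacement is 1.23 mm. The successive steps in half a period are 1.18, 0.73, 0, 0.73 and 1.18 mm, so the mean step is 3.80/5 = 0.76 mm per volume.
- One 1 mm shift at 60% of the run, otherwise still. The head spends most of the run in its first position, so the least-adjustment reference lies there. Signed mean = (300 × 1)/750 = 0.40 mm. Mean absolute displacement is also 0.40 mm. Mean step = 1/749 = 0.0013 mm per volume.

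The signed average ranks the two the wrong way round. The absolute average corrects the oscillator (1.23 mm) but leaves the settler at 0.40 mm. The step measure orders them correctly.

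**2. The same two types within a sample of 65** (600 volumes, random-walk drift with end-of-run SD 0.3 or 1.0 mm, a 2 mm oscillator, a settler shifting 1.5 or 3 mm, 300 repeats). Percentage of runs flagged on the affected parameter:

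| Score | Oscillator | Settler |
|---|---|---|
| Signed mean | 0-1% | 88-100% |
| Mean absolute displacement | 100% | 99-100% in three of four settings, 0% in one |
| Mean absolute step | 100% | 0% |

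With linear drift plus small jitter instead, and all six parameters counted, the signed rule excluded the oscillator in 73-79% of runs. Those exclusions came from the five parameters that did not oscillate. In that set-up the step rule, also tested on six parameters, flagged the settler in 18-24% of runs.

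**3. Whole-sample simulation** (65 participants, 750 volumes; log-normal jitter, jerks proportional to jitter, drift plus one step of the given SD in mm or degrees). Percentage excluded by the signed rule when drift is unrelated to jitter, with repeats under other assumed jitter in brackets:

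| Drift SD | 7 heaviest movers | Calmer half |
|---|---|---|
| 0.1 | 79 (74) | 13 (20) |
| 0.2 | 50 (37) | 28 (33) |
| 0.3 | 33 (23, 21) | 30 (33, 38) |
| 0.6 | 21 (25) | 30 (31) |

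When drift and shifts scale with each participant's jitter, the same rule excluded 58-79% of the 7 heaviest and 5-9% of the calmer half. A second set-up gave 68-80% and 5-9% across SD 0.1 to 0.6.

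**4. Share due to multiplicity.** With six independent normal averages, P(any beyond ±2 SD) = 1 − (1 − 0.0455)^6 = 24.4%, about 16 of 65. Counting the upper tail only, 1 − (1 − 0.0228)^6 = 12.9%, about 8 of 65. This arises whatever the score measures.

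**5. A single volume-to-volume score cut at 2 SD.** Total exclusions fell from roughly 23-29% (15-19 of 65) to about 5% (about 3 of 65). Two other set-ups started from 26-34% and 28-30% and also ended near 5%. The new score flagged 41-46% of the 7 heaviest movers and, in the run that reported it, none of the calmer half.

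**The case against.** **The plan may intend absolute values.** It never states how signs are handled, so a signed mean is the literal reading rather than a documented choice. If absolute values were meant, heavy movers would no longer be missed through cancellation. The settler would still usually be flagged, so the need to define the score stands either way.

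**Motion is handled elsewhere.** Despiking, censoring and motion regressors would act strongly on the oscillating trace, which is extreme: 4 mm peak to peak every 8 seconds for 10 minutes. They limit the damage from a retained mover. They do not change who is excluded, and cancellation is complete only for movement balanced about the reference.

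**The simulated misclassification is partly built in.** A reader of the table might infer that the rule works only when drift is very small, or that it reliably keeps the worst movers. Neither follows. The poor separation depends on restless participants drifting no more than calm ones. When drift tracks jitter, the signed rule separates the groups reasonably well. The documents offer nothing to choose between these assumptions.

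**The loss of calm participants is not all cancellation.** The 24.4% chance rate from six two-sided tests accounts for part of it. This objection stands.

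**Conclusion.** As written, the only participant-level motion exclusion measures mean offset from a reference image and can rank a heavy mover below a participant who settled once. That follows from the literal wording and from simple arithmetic. It is more than missing detail, since absolute values alone would not repair it.

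Its practical size is undetermined. The simulations run from near-useless separation to reasonable separation, depending on an untested link between drift and jitter. A reader might also infer that the trial's main results or the comparison between arms are distorted. The documents do not support that: the Ospan and RNT-10 primary outcomes do not use this rule, and nothing shows that it excludes differently by arm. The consequence is limited to the composition and noise of the secondary fMRI sample.

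**What to change.** In the section 9 motion paragraph, before any group-level fMRI analysis, replace the averaged parameters with the mean volume-to-volume displacement for each participant and session. One option is the Euclidean norm of the first differences of the six 3dvolreg parameters, with a stated convention for combining millimetres and degrees. Apply the exclusion to the upper tail only, and say how it works across runs and the two visits.

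The cost is about one sentence and one line of code on output that 3dvolreg already produces, with no new data. The downside should be stated openly. One score replaces six tests, so at an unchanged 2 SD the number excluded could fall a lot (in simulation, from roughly 23-29% to about 5%), and more than half of the 7 heaviest movers were retained. The cut-off should therefore be confirmed in advance for the new score, rather than carried over; an absolute limit and a maximum share of censored volumes are worth considering at the same time.

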10. HUMAN SUBJECTS

The current study will recruit 95 individuals enrolled at UCSD with a diagnosis of mood, anxiety, or traumatic stress disorder from psychiatric and primary care clinics. The study will overrecruit with the goal of randomizing 75 individuals for a final evaluable sample of 65.

Inclusion criteria will include:

- 1) age 21-55
- 2) fluent in English (sufficient to understand and complete assessments in English)
- 3) diagnosis of mood, anxiety, or traumatic stress disorder
- 4) clinically elevated repetitive negative thinking

- 5) outpatient status
- 6) 6-week stability if taking SSRI medications

Exclusion criteria will include:

- 1) past year diagnosis of severe alcohol or moderate or greater substance use disorder
- 2) lifetime history of psychotic or bipolar I disorder
- 3) acute suicidality necessitating immediate clinical intervention
- 4) neurodegenerative or neurodevelopmental disorders
- 5) history of moderate or severe traumatic brain injury or other known neurological condition
- 6) sensory deficits that would preclude completing tasks
- 7) conditions unsafe for completing MRI scanning (e.g., metal in body)
- 8) currently receiving psychosocial treatment
- 9) currently receiving psychiatric pharmacotherapy, except SSRIs

There are no inclusion/exclusion criteria pertaining to gender, ethnic background, or health status aside from MRI safety requirements stated above.

11. RECRUITMENT AND PROCEDURES PREPARATORY TO RESEARCH

Individuals will be recruited through IRB-approved announcements and advertisements posted throughout university, community settings, online media (e.g., craigslist), social media (e.g., Facebook), and ResearchMatch. The text of the proposed recruitment message is on a separate page labeled "ResearchMatch Message to Potential Participants." Individuals will also be recruited from other IRB-approved studies in the laboratory and only individuals who previously consented to be contacted for other research will be recruited. Clinical providers may be given recruitment materials to share with patients who express interest in research. All prior studies conducted in our lab ask individuals to provide written consent to be recontacted if they are interested in learning about future research by our team. Those who endorsed permission to be recontacted in these studies will be phoned and informed that there is a new study for which they may be eligible. Verbal consent will be obtained to provide information about the study and complete the screening if they are interested in participating. The investigator will make clear that this is a separate study and is completely voluntary and up to the discretion of the participant whether or not to participate.

12. INFORMED CONSENT

For the current study, all participants will undergo written informed consent. Participants will be of legal consenting age and capable of having study procedures explained to them. The IRB-approved consent form will be described with appropriate care, as documented by signature of the person giving permission.

Prior to in-person consenting, individuals will be contacted via phone for verbal consent and will be informed about the purpose of the study and asked to provide verbal consent for screening procedures. Verbal consent will be attained using the IRB approved Verbal Consent and Telephone Screening Form. Waiver of Documented Consent for recruitment screening purposes is justified because the only record linking the subject and the research would be the consent document and the principal risks would be the potential harm resulting from a breach of confidentiality. Each individual will be asked if they want documentation linking themselves with the research, and the individual's wishes will be respected. We will provide our contact information so that the individual is able to contact us at any time.

Documented informed consent will be obtained in-person at the ACTRI or via secure and HIPAA compliant telehealth during COVID-19. All procedures will follow FDA guidance ("FDA Guidance on Conduct of Clinical Trials of Medical Products during COVID-19 Public Health Emergency" and "Use of Electronic Informed Consent Questions and Answers") for participant and staff safety. To do electronic consenting, research staff will 1) identify the participant via telehealth communication, 2) review the informed consent with the participant and response to any questions the patient may have; 3) confirm that the participant's questions have been

answered; 4) confirm that the participant is willing to participate in the study and sign the informed consent document while the witness is listening via telehealth technology; and 5) obtain verbal confirmation by the patient that they would like to participate in the study. The IRB-approved consent form will be provided to participants via telehealth using the screen share function which will allow for capture of a handwritten signature on the pdf form using the stylus function. Alternatively, participants will be sent a copy of the consent form via UC San Diego Health sponsored DocuSign, after reviewing it with study staff. They will then sign the consent in real-time. The consent form will be sent to the person conducting the informed consent, who will also sign in real-time. All other elements of the consenting process will be the same as in-person.

For documented consent completed in-person, all procedures of the study, as described in the consent form, are reviewed with the prospective subject by a member of the research staff. If the individual agrees to participate, they are asked to sign the consent document and are provided a copy of the consent document and Experimental Subject Bill of Rights to keep. Consent documents will be reviewed for completeness and stored in a locked file cabinet in a locked office. Specific consent to be videorecorded will be obtained. All informed consent processes will occur in English. To participate, individuals must have sufficient proficiency in English language to understand and complete interviews, questionnaires, and all other study procedures.

13. ALTERNATIVES TO STUDY PARTICIPATION

Participants may opt not to enroll in the study.

14. POTENTIAL RISKS

Interview and Behavioral Assessments: The principal risks associated with completing the assessments are discomfort with the nature of questions, fatigue, and irritability with the testing procedure. These questions and procedures have been well-tolerated in previous studies with participant with anxiety disorders. All participants will be provided with information about local mental health resources, including information about crisis contacts.

Loss of confidentiality: By participating in this project, there is a very slight risk that sensitive personal information including psychiatric information or drug-use information which the subject has provided could become known outside the research setting. If some of the information collected, e.g. whether the subject had used illegal substances, were to become public, it may place the subject at risk for criminal or civil liability or may be hinder the subject's ability to get a job, affect his/her reputation, or have otherwise unforeseen consequences. In addition, there is some stigma associated with drug use; therefore divulging information regarding illicit drug use could be associated with adverse peer reaction. Subject information obtained during this study will remain confidential and be disclosed only with a subject's written permission.

Risks associated with functional magnetic resonance imaging: According to the FDA, there is currently no evidence that MRI with approved scanners of up to 7 Tesla signal strength are associated with adverse effects. However, there are two major sources of risk. First, the subject may experience discomfort being in the confined and sometimes noisy environment of the scanner. The main risks associated with these procedures are fatigue, boredom, and irritability with the testing procedure. The investigator and research assistants are trained to frequently check the subjects about their willingness and ability to continue with testing. If the subjects express concerns about continuing with testing, the investigator has instructed the research assistants to stop testing, offer a break, or, in case the subject is not willing to continue, to terminate the testing session. Overall, however, previous studies have not resulted in any significant discomfort or anxiety expressed by the participating subjects.

Second, the strong magnetic field and data acquisition pose some risks. These include

- The brief loud noises during the functional tasks may be physically uncomfortable.
- Physical discomfort: the subject may experience physical discomfort from being in the confined environment of the scanner for an extended period of time.

- The strong magnetic field will affect electronic, magnetic, and metal devices that subjects carry with them or that have been implanted in the subject's body. Subjects will be screened to prevent any metal from entering the scanner.
- Claustrophobia: Some subjects may get anxious in the confined space.
- Peripheral Nerve Stimulation effects: At times, some individuals may experience harmless muscle twitching or paresthesias, especially in the torso.
- Dizziness: Some individuals experience brief light-headedness while in the scanner or when rising from the MRI gurney too rapidly.
- Hearing: hearing damage may occur if appropriate hearing protection is not used because the MRI scanner produces a loud high frequency tone.

During the COVID-19 crisis, all UCSD mandates for mitigating risk of on-campus in person activities will be followed pursuant to the appropriate “phase”, including the specific guidelines established by the Keck Imaging Center where study activities take place.

15. RISK MANAGEMENT

Confidentiality (see also section 16): Confidentiality will be maintained by keeping all identifying information (such as names and phone numbers) in a separate location from the study results. Records and data will be linked to coded numbers and anonymity will be rigorously enforced. All record keeping will in accordance with the stipulations of the local Institutional Review Board. Moreover, when contacting agencies, family, or friends who were provided by the subject, no information will be provided about the nature of the participant. To minimize social and legal risk, all of the data will be kept in locked cabinets or in electronic databases with secured passwords.

Discomfort and other risks related to completing computer, behavior, and fMRI assessments: The computers will be checked regularly for proper and safe operation. Patients and comparison subjects will be carefully screened and subsequently informed about the fact that the principal investigator or delegated clinical coverage will be available at all times during the experiment. Subjects are informed that they may end the test session at any time and that participation in this research is voluntary. Examiners will be clinically trained and sensitive to signs of stress, anxiety, or fatigue so that testing will be immediately terminated should any subject experience signs of discomfort.

In terms of other fMRI related issues, to minimize the risk of fear of closed spaces while in the MR scanner, patients will be extensively interviewed and informed about the nature of the task. We have previously used pictures of the MR scanner to familiarize subjects with the scanner environment. During scanning the investigator can hear the subject at all times and if, at any point in during the scanning, the subject expresses increasing discomfort, the operator will immediately intervene and terminate the scanning procedure. There is the possibility of an abnormal finding on the fMRI scan. However, the fMRI scans are not being done for clinical purposes, and the fMRI scan procedure is not sufficient for the clinical diagnosis of a possible brain disorder. The purpose of this scan is not to diagnose abnormalities, but on rare occasions a finding is observed that might be clinically important. Should there be cause for concern, we will forward to neuroradiology. Participants will be told about the potential discomforts associated with lying in the scanner for approximately 60 minutes. During scanning, subjects' heads and necks will be supported for maximum comfort, and earplugs and headphones will be required in the MRI scanner to protect from the noise produced by the scanner. The individuals will be given an alarm button, which they will be able to press if there is any discomfort or distress. Pregnancy testing with immediate results will ensure that no pregnant individual receives an MRI. Pregnancy testing results will be discussed with participants, and counseling will be provided should the participant indicate significant distress. In order to address any concerns regarding coercion, subjects will be informed that they are free to choose not to participate and may withdraw at any time (this is included in the consent form).

Participants may terminate the study or any parts of the study at any time. During scanning the investigator can hear the subject at all times and if, at any point in during the scanning, the subject expresses increasing discomfort, the operator will immediately intervene and terminate the scanning procedure.

Procedures for ensuring professional intervention: If a participant expresses significant distress or discomfort during any study procedure, the PI will be notified. The PI (a licensed clinical psychologist) will meet with the individual to evaluate clinical status and level of risk. Subjects may be referred for intervention as deemed appropriate based on level of distress or other clinical factors. The PI will also provide appropriate referrals for outside mental health services for all consented participants, even if the participant elects not to complete the assessment. Information reported will be kept in confidence with the exception that disclosure of suicidality, homicidality, or child or elder abuse warrant reporting to appropriate authorities. In cases of clinical emergency (e.g., current risk of suicide), participants will be escorted to the Emergency Department, which is immediately adjacent to the ACTRI.

The PI will bear final responsibility for the oversight of participant safety monitoring during the study. The UCSD IRB will be provided with annual reports on recruitment, data, and adverse effects associated with the study. Any incidences of serious adverse effects will be provided to the IRB in an official report as directed by the program's current guidelines. The PI and research staff will meet weekly to address issues in recruitment, data entry and quality, training plan progress, and any clinical or adverse effects issues as they arise.

The study will have an independent safety monitor who will be responsible for ongoing monitoring of the study and reporting to the IRBs any issues regarding the safety of study participants or threats to data integrity. The monitor and research team will meet via teleconference annually (more if needed). The PI will submit the protocol for approval by the monitor prior to initiating the study activities. The monitor will document minutes from each meeting, and the PI will provide a report to the IRB each year. The monitor will review of serious adverse events (SAEs) will occur within a week of receiving any new SAE report. The safety monitor will be selected based on their experience and competencies with respect to ensuring the safety and integrity of the study. The monitor will function independently of the research team and be free of career and financial interests of the team. The monitor will possess experience in conducting clinical and/or experimental pharmacologic trials, expertise in biostatistics, and a thorough knowledge of clinical trial ethics and human subject protection issues. This monitor will not be involved in the study in any other way, and will be named and approved by the UCSD IRB prior to any initiation of study procedures.

Summary of Safety Monitor activities:

1. Safety Reporting to the safety monitor. Serious Adverse Events – Immediate review will occur for Serious Adverse Events (SAEs) – i.e., any fatal event, immediately life-threatening event, permanently or substantially disabling event, or event requiring or prolonging inpatient hospitalization. All SAEs will be required to be reported to the safety monitor regardless of any judgment of their relatedness to the study. Reporting to local IRBs will be completed within 24 hours of the SAE; reporting to the NIH will be made according to their respective regulations governing SAE reporting. Non-Serious Adverse Events – The safety monitor will be provided with annual summaries of the numbers and rates of adverse events. These reports will include types of events, severity, and intervention phase. Other Safety-Related Reports –The monitor will receive summary reports of participant retention and reasons for dropout by experimental condition (provided by [name]) and study phase.
2. Study Stopping Rules – This study will be stopped prior to its completion if there is evidence that study procedures are associated with adverse effects that call into question the safety of the procedures; recruitment or retention difficulties preclude the ability to evaluate the study endpoints; new data becomes available during the trial that necessitates stopping the trial; the safety monitor has deemed it necessary to stop the trial for any other reason out of safety or data integrity concerns.

